6.2. Adjustments for Covariates

The countries will be categorized into geographic regions for statistical analysis (Table RHBV.6.3). Unless otherwise specified, the statistical analysis models will adjust for

geographic region and baseline CRP status (nonelevated or elevated, elevated defined as >5.00mg/L).

Below are the country allocations.

Table RHBV.6.3. Geographic Regions for Statistical Analysis

Geographic Region	Country or Countries
Europe	Russia ^a , Czech Republic, Hungary, Poland, Germany, The Netherlands
Non-Europe	United States, Canada, Mexico, Japan, Korea, Taiwan

^a Russia is combined with European countries due to the small number of Russian patients and the preponderance of investigative sites in the western part of Russia.

In general, when an MMRM is to be used for analyses, baseline value and baseline-by-visit interactions will be included as covariates; when an ANCOVA is to be used for analyses, baseline value will be included as a covariate.

6.3. Handling of Dropouts or Missing Data

In accordance with precedent set with other Phase 3 axSpA trials (van der Heijde et al. 2006; Inman et al. 2008), the following methods for imputation of missing data will be used.

6.3.1. Nonresponder Imputation

Analysis of categorical efficacy and health outcome variables will be assessed using a nonresponder imputation (NRI) method. Patients will be considered nonresponders for the NRI analysis if they do not meet the clinical response criteria or have missing clinical response data at the primary analysis time point. All nonresponders at Week 16 (Visit 8), as well as all patients who discontinue study treatment at any time prior to Week 16 for any reason, will be defined as nonresponders for the NRI analysis at Week 16. Randomized patients without at least 1 postbaseline observation will also be defined as nonresponders for the NRI analysis.

The NRI may be applied at any time point specified for analysis.

6.3.2. Modified Baseline Observation Carried Forward

An mBOCF analysis will be performed on continuous efficacy and health outcome variables in the major and other secondary objectives. For patients discontinuing study drug due to an AE, the baseline observation will be carried forward to the corresponding time point for evaluation. For patients discontinuing study drug for any other reason, the last nonmissing observation before discontinuation will be carried forward to the corresponding time point for evaluation. Randomized patients without at least 1 postbaseline observation will not be included for evaluation with the exception of patients discontinuing study treatment because of an AE.

6.3.3. Last Observation Carried Forward

An LOCF analysis will be performed on continuous efficacy and health outcomes variables in the major secondary objectives. This approach is identical to the mBOCF approach, with one exception: for patients discontinuing study drug because of an AE, the last nonmissing

postbaseline observation before discontinuation will be carried forward to the corresponding time point for evaluation. Randomized patients without any postbaseline observation will not be included for evaluation.

6.3.4. Placebo Multiple Imputation

The placebo multiple imputation (pMI) method will be used for the analyses of primary efficacy endpoints ASAS40, major secondary efficacy endpoint ASAS20, and ASDAS change from baseline at Week 16 (Visit 8). [Appendix 1](#) presents the detailed scientific justification of the pMI method.

Placebo multiple imputation assumes that the statistical behavior of drug- and placebo-treated patients after discontinuing study medication becomes that of placebo-treated patients. Multiple imputations (MIs) are used to replace missing outcomes for drug- and placebo-treated patients who discontinued, utilizing multiple draws from the posterior predictive distribution estimated from the placebo arm.

Data are processed sequentially by repeatedly calling SAS® PROC MI to impute missing outcomes at visits $t=1, \dots, T$.

1. *Initialization.* Set $t=0$ (baseline visit).
2. *Iteration.* Set $t=t+1$. Create a dataset combining records from drug- and placebo-treated patients with columns for covariates \mathbf{X} and outcomes at visits $1, \dots, t$ with outcomes for all drug-treated patients set to missing at visit t and set to observed or imputed values at visits $1, \dots, t-1$.
3. *Imputation.* Run Bayesian regression in SAS® PROC MI on this data to impute missing values for visit t using previous outcomes for visits 1 to $t-1$ and baseline covariates. Note that only placebo data will be used to estimate the imputation model since no outcome is available for drug-treated patients at visit t .
4. Replace imputed data for all drug-treated patients at visit t with their observed values, whenever available. If $t < T$ then go to Step 2, otherwise proceed to Step 5. Repeat Steps 1 to 4 m times with different seed values to create m imputed complete datasets.
5. *Analysis.* For each completed dataset, use the model as would have been applied had the data been completed for continuous outcome. For the efficacy endpoints, ASAS20 and ASAS40, the missing binary outcomes will be imputed directly for each patient before fitting into the analysis model. A logistic regression model will be applied.

The final inference on treatment difference is conducted from the multiple datasets using Rubin's combining rules, as implemented in SAS® PROC MI ANALYZE.

Thus, in the effectiveness context, pMI assumes no pharmacological benefit of the drug after dropout but is a more reasonable approach than mBOCF because, unlike BOCF and mBOCF, pMI accounts for uncertainty of imputation, and therefore does not underestimate standard errors, and limits bias by taking into account study/placebo effects. In the efficacy context, pMI is a specific form of a missing-not-at-random (MNAR) analysis expected to yield a conservative estimate of efficacy.

6.3.5. Tipping Point Analyses

To evaluate the robustness of statistical analyses of key efficacy data and assumptions inherent in missing data imputation methods, tipping point analyses will be used for the missing data of ASAS40, ASAS20, as well as mean change from baseline in ASDAS at the primary time point of Week 16. [Appendix 2](#) presents the detailed scientific justification of the tipping point method.

For continuous variables (mean change in ASDAS at Week 16), a 2-step MI method is used to impute missing data independently by treatment group:

1. The first step is to create a monotone missing pattern using a Markov chain Monte Carlo method (using SAS® Proc MI with MCMC option) to handle intermittent missing data.
2. The second step is to use a set of Bayesian regressions (using Proc MI with MONOTONE option, 20 imputed data sets) for the imputation of monotone dropouts. The regression models are fit sequentially starting from the first visit with at least one missing response using treatment as a fixed effect and values (observed or imputed) from the previous visits as covariates. All patients in the ITT Population with a baseline value are included in the analyses, and all observed data are utilized from each patient, regardless of adherence to randomized treatment. A delta score is added to all imputed scores (at the primary time point) for patients in any ixekizumab treatment group in order to evaluate a scenario in which patients treated with ixekizumab would have worse outcomes than patients from the placebo. An independent delta score will be added to the placebo group and is capped for individual patients based on the range of the outcome measure being analyzed. The delta score will not be added to the observed values.

Analyses using the principal analysis model are aggregated across the m imputed data sets using SAS® PROC MI ANALYZE in order to compute a p-value for the treatment comparison for a given value of the delta score.

Sensitivity of the analysis conclusion to the choice of delta score is determined by repeating the aforementioned MI steps and analyses by gradually increasing the delta score, thus evaluating scenarios with increasingly worse imputed values for missing data for patients treated with ixekizumab. The tipping point is identified as the delta score value which leads to a loss of statistical significance when evaluating ixekizumab relative to the placebo group.

The tipping point analysis will be used for categorical data (ASAS40 or ASAS20 at Week 16) in a similar fashion:

- For ixekizumab groups, a range of response probability (for example, probability = 0, 0.1, 0.2, ..., respectively) will be used to impute the missing values for ASAS40 or ASAS20 (each probability is imputed based on 20 data sets). NRI will be used as the most extreme case.
- For placebo group, different response probability (for example, probability = 0, 0.2, ..., 1, respectively) will be used to impute the missing values for ASAS40 or ASAS20 (each probability is imputed based on m data sets).

- Analyses using the principal analysis model are aggregated across the m imputed data sets using SAS[®] PROC MI ANALYZE in order to compute a p-value for the treatment comparison for a given value of the response probability.

Sensitivity of the analysis conclusion is determined by gradually increasing the response probability value, thus evaluating scenarios with increasingly imputed response rate for patients treated with placebo. The tipping point is identified as the probability value which leads to a loss of statistical significance when evaluating ixekizumab relative to the placebo group.

6.4. Multicenter Studies

This study will be conducted by multiple investigators at multiple sites internationally. The countries will be categorized into geographic regions, as described in Section 6.2, for analysis.

For the analysis of the primary endpoint, the presence of a treatment-by-geographic region interaction will be tested at 10% significance level. Treatment group comparisons for the primary outcome will be presented separately for each geographic region. When there is evidence of an interaction ($p < .10$), descriptive statistics may be used to assess whether the interaction is quantitative (that is, the treatment effect is consistent in direction but not size of effect) or qualitative (the treatment is beneficial for some but not other geographic regions or countries).

6.5. Multiple Comparisons/Multiplicity

A multiple testing strategy for the primary and major secondary objectives will be implemented to control the family-wise type I error rate at a 2-sided α level of 0.05. The primary outcome will be tested by using the primary analysis method, logistic regression analysis with treatment, geographic region, and baseline CRP status in the model, with NRI missing data imputation approach.

A graphical multiple testing procedure (Bretz et al. 2011) will be used (Figure RHBV.6.1). The graphical approach is a closed testing procedure; hence, it strongly controls the family-wise error rate (Alosh et al. 2014). The following is a list of primary and major secondary outcomes to be tested for both ixekizumab 80 mg Q2W and Q4W regimen at Week 16:

- Primary - proportion of patients achieving an ASAS40 response [ASAS40]
- Secondary 1 - proportion of patients achieving an ASAS20 response [ASAS20]
- Secondary 2 - change from baseline in ASDAS score [ASDAS CFB]
- Secondary 3 - proportion of patients achieving BASDAI50 [BASDAI50]
- Secondary 4 - change from baseline in BASFI [BASFI CFB]
- Secondary 5 - proportion of patients achieving ASDAS inactive disease [ASDAS IN]
- Secondary 6 - change from baseline in MRI of the spine [MRI spine SPARCC CFB]
- Secondary 7 - change from baseline in SF-36 PCS score [SF-36 PCS CFB]
- Secondary 8 - change from baseline in ASAS-HI [ASAS-HI CFB].

The 8 secondary outcomes are grouped into 2 tiers ([Figure RHBV.6.1](#), [Figure RHBV.6.2](#), and [Figure RHBV.6.3](#)) based on statistical significance observed in historical axSpA studies as well as clinical and commercial relevance.

[Figure RHBV.6.1](#) shows the graphical testing scheme with initial α allocation and weights, and [Figure RHBV.6.2](#) and [Figure RHBV.6.3](#) show the graphical testing schemes used within the Tier 1 and Tier 2 groups of endpoints respectively. The testing steps are outlined below:

[figure not shown]
Step 1: The primary outcome of ASAS40 will be tested for ixekizumab 80 mg Q2W vs. placebo at a two-sided $\alpha=0.05$. If the null hypothesis is not rejected, no further testing is conducted as the α for that test is considered ‘spent’ and cannot be passed to other endpoints. If the null hypothesis is rejected, then move to Step 2.

Step 2: The primary outcome of ASAS40 will be tested for ixekizumab 80 mg Q4W vs placebo at a two-sided $\alpha=0.05$. If the null hypothesis is not rejected, no further testing is conducted as the α for that test is considered ‘spent’ and cannot be passed to other endpoints. If the null hypothesis is rejected, then move to Step 3.

Step 3: $\alpha=0.025$ will be distributed to Tier 1 set of secondary outcomes for ixekizumab 80 mg Q2W (blue circles in [Figure RHBV.6.2](#)), and the remaining $\alpha=0.025$ will be distributed to Tier 1 set of secondary outcomes for Ixekizumab 80 mg Q4W (green circles in [Figure RHBV.6.2](#)).

[figure not shown]
The major secondary endpoints for both doses will be tested according to the procedure specified by the graphs.

The testing process continues for the remaining outcomes by allocating the remaining α to the next set of outcomes as long as at least one hypothesis can be rejected. Each time a hypothesis is rejected, the graph is updated to reflect the reallocation of α , which is considered “recycled” (Alosh et al. 2014). This iterative process of updating the graph and reallocating α is repeated until all major secondary hypotheses have been tested or when no remaining hypotheses can be rejected at their corresponding α level. The weights along the edges for α allocation between ixekizumab 80 mg Q2W and ixekizumab 80 mg Q4W outcomes as well as within each of the tiers are prespecified in [Figure RHBV.6.1](#), [Figure RHBV.6.2](#), and [Figure RHBV.6.3](#).

[figure not shown]
Abbreviations: ASAS = Assessment of Spondyloarthritis International Society (ASAS); Q2W = every 2 weeks; Q4W = every 4 weeks.

Figure RHBV.6.1. Illustration of graphical multiple testing procedure with initial α allocation and weights.

Abbreviations: ASAS = Assessment of Spondyloarthritis International Society; ASDAS = Ankylosing Spondylitis Disease Activity Score; BASDAI = Bath Ankylosing Spondylitis Disease Activity Index; BASFI = Bath Ankylosing Spondylitis Functional Index; SF-36 PCS = Short Form 36 physical component score; CFB = change from baseline; Q2W = every 2 weeks; Q4W = every 4 weeks.

Figure RHBV.6.2. Graphical multiple testing scheme used within the Tier 1 group of endpoints.

Abbreviations: MRI spine SPARCC = MRI of spine Spondyloarthritis Research Consortium of Canada score; ASDAS IN = ASDAS inactive disease; ASAS-HI = ASAS Health Index; CFB = change from baseline; Q2W = every 2 weeks; Q4W = every 4 weeks.

Figure RHBV.6.3. Graphical multiple testing scheme used within the Tier 2 group of endpoints.

There will be no adjustment for multiple comparisons for any other analyses.

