#### **9.2.6. Adjustment for Multiple Comparisons**

A multiple testing strategy for the primary and major secondary objectives will be implemented to control the overall family-wise type I error rate at a 2-sided  $\alpha$  level of 0.05. A graphical multiple testing procedure (Bretz et al. 2011) will be used (Figure RHBV.2). The graphical approach is a closed testing procedure, hence it strongly controls the family-wise error rate (Alosh et al. 2014). The following is a list of primary and major secondary outcomes to be tested for both ixekizumab 80 mg Q2W and Q4W regimens at Week 16:

[figure not shown]
- Primary: proportion of patients achieving an ASAS40 response [ASAS40]
- Secondary 1: proportion of patients achieving an ASAS20 response [ASAS20]
- Secondary 2: change from baseline in ASDAS score [ASDAS CFB]
- Secondary 3: proportion of patients achieving BASDAI50 [BASDAI50]
- Secondary 4: change from baseline in BASFI [BASFI CFB]
- Secondary 5: proportion of patients achieving ASDAS inactive disease [ASDAS inactive]
- Secondary 6: change from baseline in MRI of the spine [MRI spine SPARCC score CFB]
- Secondary 7: change from baseline in SF-36 PCS score [SF-36 PCS CFB]
- Secondary 8: change from baseline in ASAS-HI [ASAS-HI CFB]

The 8 secondary outcomes are grouped into 2 tiers (Figure RHBV.2) based on the clinical importance as well as statistical significance observed in historical axSpA studies.

Figure RHBV.2 shows a general form of the graphical testing scheme. The primary outcome of ASAS40 will be tested for ixekizumab 80 mg Q2W versus placebo at a 2-sided  $\alpha=0.05$ . If the null hypothesis is not rejected, no further testing is conducted as the  $\alpha$  for that test is considered

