“spent” and cannot be passed to other endpoints. If the null hypothesis is rejected, the  $\alpha$  will be distributed to the Tier 1 set of secondary outcomes for ixekizumab 80 mg Q2W and ASAS40 for ixekizumab 80 mg Q4W. The testing process continues for the remaining outcomes by allocating the remaining  $\alpha$  to the next set of outcomes as long as at least one hypothesis can be rejected. Each time a hypothesis is rejected, the graph is updated to reflect the reallocation of  $\alpha$ , which is considered “recycled” (Alosh et al. 2014). This iterative process of updating the graph and reallocating  $\alpha$  is repeated until all major secondary hypotheses have been tested or when no remaining hypotheses can be rejected at their corresponding  $\alpha$  levels. The weights along the edges for  $\alpha$  allocation between ixekizumab 80 mg Q2W and ixekizumab 80 mg Q4W outcomes as well as within each of the tiers will be prespecified in the SAP prior to the first patient randomization of the study.

Abbreviations: ASAS = Assessment of Spondyloarthritis International Society; ASAS HI = ASAS Health Index; ASDAS = Ankylosing Spondylitis Disease Activity Score; BASDAI = Bath Ankylosing Spondylitis Disease Activity Index; BASFI = Bath Ankylosing Spondylitis Functional Index; CFB = change from baseline; SF-36 PCS = Short Form 36 physical component score; SPARCC = Spondyloarthritis Research Consortium of Canada; Q2W = every 2 weeks; Q4W = every 4 weeks.

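### Does SAP 6.5 wrongly close the Q2W secondaries when Q4W ASAS40 fails, where Protocol 9.2.6 would leave them open?

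*SAP*

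**What the plan says.** Protocol 9.2.6 starts with Q2W: "The primary outcome of ASAS40 will be tested for ixekizumab 80 mg Q2W versus placebo at a 2-sided" level of 0.05, and testing ends if that hypothesis stands. If it is rejected, alpha "will be distributed to the Tier 1 set of secondary outcomes for ixekizumab 80 mg Q2W and ASAS40 for ixekizumab 80 mg Q4W". Testing then passes "to the next set of outcomes as long as at least one hypothesis can be rejected". The same section says that its figure "shows a general form of the graphical testing scheme", and that the weights on the arrows between the two regimens "as well as within each of the tiers will be prespecified in the SAP".

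SAP 6.5 sets the order out in three steps. Step 1 is Q2W ASAS40 at 0.05. The next reads "Step 2: The primary outcome of ASAS40 will be tested for ixekizumab 80 mg Q4W vs placebo at a two-sided" level of 0.05, with its own stop: "If the null hypothesis is not rejected, no further testing is conducted". Only at Step 3, after both have been rejected, is alpha divided: 0.025 "will be distributed to Tier 1 set of secondary outcomes for ixekizumab 80 mg Q2W", and 0.025 to the Q4W Tier 1 set.

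**The concern.** Take the outcome in which Q2W beats placebo on ASAS40 and Q4W does not. On the protocol's wording, the Q2W Tier 1 secondaries have received some alpha and can still be tested. On the SAP's wording they have received none, and testing is over for both regimens. The same data would then support two different sets of confirmatory Q2W claims, depending on which document is read.

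The SAP revision history (Section 3) does not remove the doubt. Its Version 2 entry for Section 6.5 mentions revised weights and the order of secondary outcomes within tiers, not a new stop. The list of changes since Version 2 has no entry for Section 6.5. Version 3 was approved after unblinding, so a reader may reasonably ask when the Step 2 stop came in.

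**Working it through.** **1. The two rules on the discordant outcome (Q2W ASAS40 rejected, Q4W ASAS40 not).**

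| | Protocol 9.2.6 | SAP 6.5 |
|---|---|---|
| Alpha to Q2W Tier 1 after Q2W ASAS40 | a share of 0.05, size not stated in the text | 0 |
| Alpha to Q4W ASAS40 | the remainder | 0.05 |
| Q2W Tier 1 still testable? | yes, on its wording | no |

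In a graphical procedure, the weights leaving a hypothesis are non-negative and sum to at most 1. The SAP's order is weight 1 on the arrow to Q4W ASAS40 and weight 0 on the arrow to Q2W Tier 1. Strong control holds under either choice. At Step 3 the split is 0.025 + 0.025 = 0.05, so no alpha is created.

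**2. Reproducing the plan's power.** Inputs from SAP 5.3 and Protocol 9.1: 80 per arm, 44% on Q2W, 16% on placebo, two-sided Fisher's exact test at 0.05. Exact enumeration over Binomial(80, 0.44) × Binomial(80, 0.16) gives 96.7%. The pooled normal approximation gives 97.7%. Both agree with the stated figure of about 96%.

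**3. How often the rules can disagree.** Let x₀ be the placebo count. Let w(x₀; p) be the chance that an arm with response rate p gives two-sided p ≤ 0.05 in the favourable direction against x₀. With a shared placebo arm,

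P(Q2W wins, Q4W fails) = Σ Bin(x₀; 80, 0.16) · w(x₀; 0.44) · [1 − w(x₀; p₄)].

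The documents give no Q4W rate p₄, so it is an assumption, shown over a range. The Wald column uses the unadjusted log odds ratio, with Fisher's test where a cell is zero. The SAP's covariate-adjusted logistic model is not reproduced.

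| Assumed Q4W rate | Q2W wins, Q4W fails (Wald) | Same (Fisher) | Both win (Fisher) |
|---|---|---|---|
| 48% | 0.4% | 0.7% | not computed |
| 44% | 1.9% | 2.7% | 94.0% |
| 40% | 6.2% | 8.1% | 88.6% |
| 36% | 15.7% | 19.3% | 77.4% |

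Check at 44%: 0.0269 + 0.9403 = 0.9672, which agrees with the Q2W power of 0.9671 up to rounding.

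These are upper limits on differing claims, because the disagreement has an effect only if a Q2W Tier 1 test would also be significant.

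**4. What the SAP's order buys.** Any positive share to Q2W Tier 1 means that Q4W ASAS40 is first tested below 0.05. Take an even split, 0.025, purely as an illustration. By Fisher's test, the chance that Q2W wins and Q4W misses at that first look is 4.96%, 13.19% and 27.98% for Q4W rates of 44%, 40% and 36%. The chance that both win is then:

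- 44%: 96.71 − 4.96 = 91.75%, against 94.0% under the SAP
- 40%: 96.71 − 13.19 = 83.52%, against 88.6%
- 36%: 96.71 − 27.98 = 68.73%, against 77.4%

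Recycled alpha from Q2W Tier 1 could recover part of that loss. The direction is plain: the SAP protects the second primary comparison at the expense of the Q2W secondaries.

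**The case for a change.** The strongest case for acting is that the protocol delegates weights, not recipients. It names the Q2W Tier 1 secondaries as receiving alpha. A zero weight takes a named recipient off the list and adds a stop that the protocol does not state. Without a sentence saying which rule governs, the more permissive protocol text stays available to anyone who wants to claim Q2W secondaries after a Q4W failure.

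Part of this stands. The wording of the two documents does differ, and the natural reading of the protocol sentence is a split with something for each recipient. The discordant outcome is also not negligible if Q4W is modestly weaker.

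The rest is less firm:

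- The protocol sets no minimum weight and describes its scheme as general. The figures that carry the arrows (Protocol Figure RHBV.2, SAP Figures RHBV.6.1 to 6.3) are not visible in the available text, so the protocol's intended split cannot be read.
- The protocol's sentence on continuing while something can still be rejected does not show that a second stop is excluded. SAP 6.5 carries the same sentence after its own Step 2 stop.
- A governing rule is not really absent. Protocol 9.2 sends the full detail of the analyses to the SAP, and SAP 6.10.1 and 6.10.2 tie the primary and major secondary tests to Section 6.5. Protocol 9.4.2.1 does point back to 9.2.6, but 9.2.6 defers to the SAP for the weights.
- On the log as written, the Step 2 stop dates from Version 1 (7 April 2016, before the first patient visit) or from the weight revision in Version 2 (19 January 2018, before the first unblinding). No entry suggests that it was chosen after unblinding.

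**Conclusion.** This is a difference of wording that the plan's own delegation resolves, in the conservative direction. An analyst who follows SAP 6.5 gets a valid confirmatory result with the family-wise error rate held at 0.05. The primary objective in both documents is to compare both regimens with placebo on ASAS40, so completing those two tests before any secondary is a fair trade-off. Moving the SAP to the protocol's split is not attractive either, since Version 3 was approved after unblinding.

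The practical reach is small. At 44% on both regimens, the two rules can differ in 1.9 to 2.7% of trials at most. The larger figures, 6.2 to 19.3%, need an assumed Q4W rate of 40% or 36%, for which the documents offer no support. Protocol 4.3 expects full or nearly full effect by Week 16 on both regimens, which favours the lower figures without proving the effects equal.

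What remains is a reporting matter. The clinical study report should say that SAP 6.5 was the sequence used, how it departs from the wording of Protocol 9.2.6, and in which SAP version the Step 2 stop was adopted. Protocol 9.2 already asks for changes of method to be described and justified there, so nothing in the plan needs to change.
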